2 INTRODUCTION

2.1 STUDY RATIONALE

Three pilot studies of evaluating use of the traditional ketogenic diet in PD have been reported. They showed either reduction in UPDRS, particularly non motor greater than motor scores (Van Itallie 2005, Phillips 2018), or improved cognition (Krikorian 2019). These studies all had limitations, in part related to pilot outpatient design, with gaps or deficiencies identified in the following: monitoring for adherence and reliability of the intervention; degree of ketosis attained; frequency of testing for ketosis; frequency of outcome assessment to obtain adequate signal : noise ratio with respect to biological fluctuations in the disease; reliability of UPDRS rating scale used as primary outcome for small cohort groups; lack of quantitative testing of cognitive and motor functions in the same cohort for comparison; lack of testing for disease mechanism engaged that might account for the proposed benefits.

VanItallie et al reported results of an unblinded, at-home ketogenic diet for 28 days in terms of pre vs. post UPDRS scores of 5 individuals with PD (from 7 with 2 dropouts), 4/5 with Hoehn & Yahr stage 3, who had varying degrees of ketosis mostly high therapeutic range of beta-OHB levels reported (4.8 – 8.9 mM) and one outlier range 1.13 – 1.56 mM). All five participants had decline in total UPDRS score, mostly (4/5 participants) being 21-46% from baseline. There were clear study limitations of placebo effect in study lacking a control group; lack of rater blinding and placebo control; lack of reliable ketosis monitoring aside from infrequent (unreported frequency) serum betaOHB, whereas daily ketone measurement was only urine dipstick and therefore qualitative; lack of monitoring of the diet relying primarily upon self-report via telephone and intermittent patient visits to the dietician; limited study size, and strict 4:1 standard ketogenic diet regimen with 2 drop outs of 7 participants and additional 2/5 remaining participants with reported dietary relapse.

Phillips et al addressed some of these issues by comparing two randomized groups, a comparatively less stringent ketogenic diet vs. a low-fat diet prescribed by meal plans, each with approximately 18% protein and either 79% lipid / 3.7% net carb (KD) or 23% lipid / 59% net carb (low-fat diet), the latter also with greater dietary fiber, stratified by estimated daily energy expenditure, for longer duration (8 weeks) and checking for ketosis monitoring by daily (AM fasting) beta-OHB levels by a validated fingerstick ketone meter as well as monitoring adherence through daily ticking of meal plans that were outlined for the entire study period. However, this study also had some limitations including infrequent data capture and diet monitoring relying upon self-report, precluding correlative analysis between ketosis value and clinical rating scale (UPDRS) performed only pre vs. post intervention. Another possible limitation was mean beta OHB level being only 1.19 in the KD group, if greater degree of ketosis might be beneficial.

Krikorian et al evaluated another less stringent ketogenic diet in a PD cohort with mild cognitive impairment (unlimited protein, <20g carb target), recognizing that impaired glucose tolerance / metabolic syndrome is a risk factor for higher comorbidity in PD than in the general population, and that the literature supports ketogenic diet as a therapy specifically for metabolic syndrome (Hyde et al, 2019). They similarly used pre vs. post intervention data capture of 8 weeks duration, assessing cognition as well as UPDRS, and the dietary manipulation of only carbohydrate may provide a more feasible approach with lower level of change required for participants, however even the less prescriptive guidelines were not exactly adhered to. They followed 10 subjects in KD group vs. 7 in low-fat group, however they reported low level ketosis (mean beta-OHB 0.31 mM by study end week 8) in the low carbohydrate group and mean carb daily intake of 36g (above 20g) in that group. Dietary monitoring was done by patients filling out three-day diaries in each study week. Interestingly, despite the low ketosis values they nonetheless found improvement in short-term memory and verbal fluency in the KD group compared to the high

Abbreviated Title: Tolerability and efficacy of ketogenic diet in Parkinson's Disease**Version Date:** 04/19/2021

carbohydrate diet despite no motor differences on UPDRS-III or finger tapping speed, which raises the question of does ketosis matter for symptom improvement (whether cognitive or motor) in PD, as opposed to effects of lipid, carbohydrate or protein metabolism, such as improved insulin sensitivity / insulin brain signaling and increased BDNF expression, benefits attributed to ketogenic diet (please refer to Section 3.2.1 for details) but not specific to it. The question of macronutrient ratio contribution to the cognitive benefit in the study was not tested, and such comparison was not available given that all three macronutrient groups varied proportionally between the two groups. For instance, mean protein intake, which was not controlled, was higher in the low carbohydrate group (123 g vs. 89 g in the high carbohydrate group). Lack of controlling for protein intake appears to be a confounding issue for Parkinson's studies given the results confirmed in multiple studies of levodopa absorption being affected by food intake, for instance large neutral amino acid L-leucine decreased intestinal absorption of levodopa by ~50% in healthy subjects (Lennernäs et al, 1993), which is meaningful particularly in moderate to advanced PD where dopamine-responsive fluctuations occur coupled with the pharmacokinetics of levodopa concentrations, and a single load of 0.4 g protein / kg body weight diminished response of levodopa in PD patients with motor fluctuations (Mena and Cotzias 1975; Nutt et al 1984; Juncus et al 1987; Pincus and Barry 1987).

These limitations form the primary impetus behind the current study. The inpatient design is well suited for a pilot feasibility study, as it offers advantages in providing optimal adherence monitoring and generation of a time series through frequent ketosis values compared to symptom monitoring including repeated clinical, physiology, and cognitive tests that would be more difficult or simply not feasible in the outpatient setting. The overall goal is to test metabolic measures of a standard ketogenic diet with MCT oil supplement in an effort to improve upon feasibility issues identified in the other studies. A corollary objective is to test the effects of ketosis on symptom measures by comparing MCT-KD to a standard, American diet. The following table outlines macronutrient composition of diets proposed for study (italicized) and other diets with available data on ketogenesis or use in PD. While the proposed KD matches others such as Phillips et al in proportion of energy supply from lipids of around 80%, the addition of MCT supplement to replace a portion of the 80% lipids may be a useful adaptation, similar to a study in healthy volunteers that showed more rapid keto-induction and less keto-induction symptoms (Harvey et al, 2019) in order to better and more expeditiously achieve the primary objective of ketosis feasibility.

Table 1 – macronutrient ratios of different diets used in clinical research for PD / other neurologic disorders

	Modified MD-KD (MMKD)	MCT diet	KD*	SAD (high carb diet)	MD	LFD, aka AHAD
Lipid	60-70%	45-70%	80%	30-40%	45-50%	15-20% (<7% saturated, <300mg cholesterol daily)
Protein	25-30%	10-20%	10-15%	15%	15-20%	20-30%

Abbreviated Title: Tolerability and efficacy of ketogenic diet in Parkinson's Disease**Version Date:** 04/19/2021

Net Carb	5-10%, max 30 g	10-35%	5-10%	45-55%	30-40%	55-65%
Comment	Studied 12 weeks in obesity (Perez-Guisado et al 2008); in MCI/CN/SM C (Neth et al 2020)	Improved compliance in pediatric epilepsy (Liu et al 2008)	Studied in PD VanItallie et al 2005; Phillips et al 2018; in obesity/MetSx (Hyde et al, 2019); 8 weeks in PD-MCI Krikorian et al 2019	As defined by Stephen Phinney; studied by Krikorian et al, 2019	Widely considered to be rich in vitamins/mineral, less risk of deficiencies	Studied as control group in Phillips et al 2018; Neth et al 2020). AHA Guidelines: rich in fruit/vegetable, whole grains, fish 2+ meals/ week, minimize added sugars,
Ketosis values	Mean 0.31 mM (Krikorian MCI cohort) 0.7 mM (Neth et al – 1.0 mM in SMC vs 0.4 mM in MCI)	Mean increase beta-OHB by 0.7 mM by study day 8-9 of 20 randomized 30mL TID MCT vs. LCT, sunflower oil (Harvey et al, 2019)	Mean AM fasting betaOHB 1.15 mM vs. 0.16 mM in LFD (Phillips et al, 2018)	0 to 0.2 mM (daily fasted state)	No data found	0 to 0.2 mM (daily fasted state)
Glucose / other ancillary data	Glucose decrease by 16 mg/dL (109 to 93) Perez-Guisado 2008; decrease TG (-23 mg/dL) and VLDL (-4.6 mg/dL) increase LDL 17 mg/DL; body weight loss greater than AHAD (Neth et al)		In cohort with MetSx x 4 wks: Reduction of glucose -10 mg/dL, TG -60 mg/dL, dense LDL, plasma total saturated fat, increased HDL (+4 mg/dL), arachidonate compared to medium-carb and high carb diets (Hyde et al, 2019) Increased HDL, LDL, no difference TG compared to LFD (Phillips et al, 2018). HbA1c trend not statistically significant.		Reduced risk of prodromal PD in a populational cohort in Greece (Maraki 2019); consistently reduced LDL, central obesity and Met Sx (Babio et al 2014 PREDIMED trial); many studies with reduced CV risk reduced mortality (Bo et al 2016)	In 20 HV: No change in LDL, HDL, TG in 4 mo. crossover study compared to decline in LDL & TG and increase in HDL after 4 mo. Paleolithic diet (40% lipid, 23% carb, 37% protein -- no dairy, grains, legumes, daily: <1/2 cup potato, <1oz dried fruit, <4oz wine daily, unlimited eggs) (Pastore et al, 2015)
Keto-induction symptoms / side effects	Attrition rate 22.5% (Perez-Guisado), 10% Neth et al and Nagpal et al for MMKD vs. 5% for	Shortened keto-induction (0.5 mM) from day 5 to day 3, vs LCT (sunflower) oil; decrease overall keto-induction symptoms but	Attrition rate 28% VanItallie et al, 18% Phillips et al (9% attributed to diet). No major adverse event. Initial symptoms of increased			

Abbreviated Title: Tolerability and efficacy of ketogenic diet in Parkinson's Disease

Version Date: 04/19/2021

	AHAD. No adverse event occurred in any study.	increased GI symptoms; reduced incidence kidney stones, hypoglycemia, ketoacidosis, constipation in pediatric epilepsy cohort (Liu et al, 2006)	tremor/rigidity irritability, hunger, thirst were self-reported at higher frequency in KD weeks 1-4. All sx's normalized in weeks 5-8 compared to LFD aside from excessive thirst (5/22).			
*While ketogenic diet macronutrient ratios vary between studies, the targets are similar to those used in prior KD study in PD, Phillips et al, presumably better tolerated than strict 4:1 KD, and is proposed for the current ketogenic diet study.						

Despite the limitations of low subject numbers and infrequent data capture, these previous trials of nutritional ketosis in Parkinson's suggest motor, cognitive and non-motor symptom benefit, particularly in symptoms including fatigue, depression, and urinary frequency, in comparison to high carbohydrate, low fat diets even at moderate reported ketosis values of 0.3-1.0 mM. The mechanisms and specific biomarkers of PD impacted by ketogenesis have not yet been defined, nor the time course of any effects. Furthermore, adherence as well as side effects related to micronutrient deficiency or extreme skew of macronutrient composition towards lipids remain barriers to wider adoption of studying ketogenic diet for treating PD. MCT ketogenic diet (MCT-KD) may require less stringent carbohydrate restriction and fewer micronutrient supplements than classic KD; may improve tolerability (Liu 2008); and has been shown to augment mean levels of ketosis in healthy volunteers (Harvey 2018). MCT-KD remains unexplored in PD, particularly as synergistic therapy. In this clinical study, an inpatient pilot design is proposed to study the effects of a carbohydrate-restricted ketogenic diet supplemented by MCT oil nutritional ketosis vs a standard non-ketogenic, low fat diet (SAD), within the keto-induction period and shortly thereafter over one week, on brain network connectivity via EEG cortico-cortical connectivity and motor waveform characteristics, motor physiology and clinical scale (UPDRS), cognition, autonomic function (heart rate variability, orthostatic blood pressure) and symptoms of PD with fingerstick beta-OHB levels and respiratory exchange ratio (RER) in the Metabolic Unit +/- continuous glucose monitoring (CGM) to establish which, if any, PD symptoms may be modulated by ketogenic intervention in relation to suspected or likely metabolic pathways, to inform subsequent study into symptomatic benefit and/or disease modification. To better address the primary aim of diet feasibility, a two-week outpatient segment is proposed to assess more long-term effects of a similar ketogenic diet and further estimate adherence using an online, web-based application.

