4. STUDY DESIGN

4.1 OVERALL DESIGN

The experiment will take place predominantly in the Metabolic Unit, 7SW-S (1-week inpatient) and at home (2 weeks outpatient). Additionally, EEG, TUG, and heart rate variability tests will be performed in the HMCS labs within the 7SW-Neurotesting area.

This study is a single center (NIH Clinical Center), phase 1 feasibility/tolerability assessment of MCT oil subtype of ketogenic diet in a PD cohort, randomized, double-blinded vs. standard American (high-carbohydrate) diet based on macronutrient percentages of calculated daily energy expenditure using measured pCO₂ and pO₂ and Weir formula for indirect calorimetry, performed on screening visit, to give caloric macronutrient ratios 50-55% carb, 35% lipid, 10-15% protein in SAD group and 5-10% carb, 80% lipid, 10-15% protein in MCT-KD group on the 7SW-S Metabolic Unit with assistance of CC Nutrition Department staff. Consent, baseline lipid panel, BMP, and pregnancy test will be done at screening visit. Randomization will occur upon screening visit, stratified by age ≥ 65 or < 65 and baseline TUG score ≥ 11.5 s or < 11.5 s. Protein macronutrient percentage of individual calculated daily energy intake will be the same between the two groups. Diet will be within subject factor for both groups, as pre-diet intervention baseline testing is planned for hospital day #1. The potential confound of changes in activity/exercise level while in the hospital on physiologic and clinical outcomes is recognized. To address this, study investigators will form an individualized exercise plan incorporating baseline exercise and activity levels to involve stationary bike at target HR based on age-adjusted HR max target using Tanaka's formula validated in the elderly population, $208 - 0.7 \times \text{age}$, in order to approximate each participant's daily baseline intensity levels from questionnaires.

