Abbreviated Title: Tolerability and efficacy of ketogenic diet in Parkinson's Disease

Version Date: 04/19/2021

often to prescribe the diet for a period of time such as 6 months or 1 year because the therapeutic benefit of seizure reduction/cessation often endures long after switching back to a regular diet, such data are not available for Parkinson's and will require further study, which this study does not attempt to address. Rather, this study proposes to address what level of ketosis can be achieved through an MCT oil supplemented, monitored diet with less stringent carbohydrate restriction and therefore presumably better tolerated as a long-term therapy; whether there may be particular biomarkers to indicate success of the diet, such as EEG central beta power, heart rate variability or BDNF; if side effects of MCT oil are tolerable in this population with known gastro-intestinal paresis; and what effect does a given ketosis value have compared to another on serially repeated, validated measurements in PD.

Anecdotally, PwP adhering to ketogenic diet or other low-carbohydrate diets such as Paleolithic diet have reported that both diets, avoiding carbohydrate and large amounts of protein, improve symptoms such as walking speed, tremor and fatigue, even at low or undetectable values of ketosis as measured from a ketone meter reagent strips, a validated method for beta-OHB levels 0.1 – 6.0 mM (for further details of community engagement please refer to section 5.6). Accordingly, the mechanism underlying benefits of a low carbohydrate diet appears to be more multifaceted than simply ketosis, potentially involving differences related to fatty acid metabolism, levels of PUFA (polyunsaturated fatty acids), glycolysis, insulin sensitivity, levels of antioxidants, DNA repair, and buffers for coenzyme activation. This remaining question drives the study, with the question of “do ketosis values matter,” which is well posed for inpatient metabolic unit study.

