4.3 JUSTIFICATION FOR DOSE

MCT ketogenic diet has been shown to be non-toxic (Traul 2000) and well tolerated at a dose of 30mL three times daily (Harvey et al 2018). This dose led to a mean increase in beta-OHB of 0.8mM by day 7 and shorter latency of keto-induction (more participants achieving level of 0.5mM by days 1-2), as well as lower mean glucose values, with mean beta OHB in the MCT oil group >1mM by day 6. Due to the reported higher incidence of GI side effects in that study, and expected lower GI motility due to autonomic dysfunction, a more moderate dose of 20% calculated daily resting energy expenditure or approximately 45-60 mL daily will be used. A similar dose of 40mL once daily in a cohort of AD participants the morning fasted state showed increase of beta-OHB by approximately 0.5mM at peak-dose, 90 minutes later (Reger et al, 2004). MCT as a supplement to ketogenic diet has also been studied in pediatric epilepsy and found to be useful to achieve a therapeutic effect in that population with a wider range of carbohydrate intake (reviewed in Liu et al, 2008). A similar use in PD might be established, and such determination would require further study such as proposed in this study. MCT permits a manipulation of ketogenesis between a ketogenic and non-ketogenic group while maintaining a similar diet composition, including same levels of protein, which is an important potential confound through its reported effect on L-DOPA intestinal absorption neutral large amino acid transporter.

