1 STATISTICAL CONSIDERATIONS

9.1 STATISTICAL HYPOTHESIS

Primary hypothesis:

Nutritional ketosis supplemented by MCT oil is feasible within a Parkinson Disease cohort as defined by an acceptable retention rate and outpatient adherence.

Primary outcome: Feasibility of nutritional ketosis(ketogenic diet with 80% lipid including MCT oil, 10-15% protein, 5-10% carbohydrate), in Parkinson Disease cohort defined as a composite outcome meeting all of the following criteria: recruitment target of 32 or as per interim power analysis defined in Section 9.4.6; retention rate > 80% at study end; adherence to ketogenic diet in the outpatient portion defined as mean carbohydrate energy intake <10%, and intervention is acceptable to all participants by Likert scale \geq 2/4 of likelihood of using this therapy in the future and effectiveness in symptom reduction, from all study participants at 3 weeks.

Secondary hypothesis:

Abbreviated Title: Tolerability and efficacy of ketogenic diet in Parkinson's Disease

Version Date: 04/19/2021

Nutritional induced ketosis (NK) increases mobility based on TUG score in a Parkinson Disease cohort at 7 days compared to usual diet (35% lipid, 10-15% protein, 50-55% carbohydrate). Secondary outcome: timed Up & Go test (TUG score) at study day 7 (fastest of three trials)

$H_0: \mu_1 = \mu_2$, where μ_1 and μ_2 are the population means for the NK diet group and usual diet group respectively vs. $H_1: \mu_1 \neq \mu_2$.

Exploratory hypotheses:

Hypothesis A: Nutritional ketosis improves PD symptomatology in cognition (improved attention, recall, and executive function, and motor function akinesia and tremor within six days, as assessed by: Stroop word-color interference latency (executive function), n-back recall task (attention and working memory), simple reaction time (akinesia); fingertap speed and rhythm MN and PQ keyboard tasks (fine motor), and autonomic function (heart rate variability at rest and with deep breathing / Valsalva Maneuver tests)

Hypothesis B: The mechanism of symptomatic reduction of NK in PD is both augmented mitochondrial metabolism (direct, rapid) and augmented neurotransmitter and growth factor synthesis (indirect, delayed), especially GABA and dopamine, as assessed by resting state EEG spectral power, phase coherence, and M1 waveform normalization. Accordingly, effect sizes for exploratory outcomes will be greater at 3 weeks than 7 days.

Exploratory outcomes daily (days 1-7), week 3

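### The randomised MCT-KD versus SAD comparison estimates a whole-diet effect; the wording that it tests ketosis, at similar diet composition, is wrong except for matched protein and energy

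*Combined protocol and SAP*

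**What the plan says.** - **Purpose of the comparison (Section 2.1):** "A corollary objective is to test the effects of ketosis on symptom measures by comparing MCT-KD to a standard, American diet".
- **The fault found in an earlier trial (Section 2.1):** in an earlier PD trial of a low-carbohydrate diet, the contribution of macronutrient ratio could not be examined; "such comparison was not available given that all three macronutrient groups varied proportionally between the two groups".
- **The driving question (Section 4.2):** "This remaining question drives the study, with the question of" whether ketosis values matter.
- **The claimed property of MCT (Section 4.3):** "MCT permits a manipulation of ketogenesis between a ketogenic and non-ketogenic group while maintaining a similar diet composition", with equal protein given as part of that similarity.
- **The arms (Section 4.1):** "50-55% carb, 35% lipid, 10-15% protein in SAD group and 5-10% carb, 80% lipid, 10-15% protein in MCT-KD group". Section 1.1 adds that the diets are isocaloric with the same protein ratio.
- **The TUG hypothesis (Section 9.1):** "Nutritional induced ketosis (NK) increases mobility based on TUG score in a Parkinson Disease cohort at 7 days", compared with usual diet. The secondary objective in Section 1.1, the exploratory objectives in Section 3 and the hypothesis in Section 4.1 also name nutritional ketosis as the cause. Section 4.1 expects part of the effect within hours of reaching ketosis.
- **The analysis (Section 9.4.2):** an ANCOVA of day-7 TUG with age and day-1 TUG as covariates, described as evaluating the effect of diet.

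**The concern.** Section 2.1 faults an earlier trial because its arms differed in every macronutrient, so a benefit could not be traced to ketosis. This trial fixes protein but leaves fat and carbohydrate far apart, and the fat in one arm includes a large MCT component. Ketosis, carbohydrate restriction, high fat intake and MCT intake all change together with the randomised arm.

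What is at stake is what may be concluded from the day-7 TUG result. Rejecting the null would confirm the Section 9.1 sentence as written, that ketosis increases mobility, although the randomisation supports only a statement about the diet. A null result has the same limit. Section 4.1 itself reasons that dietary fat may lower and delay peak levodopa and so bias towards no difference. That route works through fat, not ketones, so a null result would not show that ketosis has no effect.

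**Working it through.** **1. Gap between the arms.** MCT-KD is 80% lipid and 5-10% carbohydrate wherever its full targets are given (Sections 4.1, 6.1.1, 6.1.2.1, 9.1). The SAD figures vary. Lipid gap = 80 minus SAD lipid. Carbohydrate gap = SAD carbohydrate minus 10 (smallest) or minus 5 (largest).

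| Source of SAD figures | SAD lipid | SAD carbohydrate | Lipid gap | Carbohydrate gap |
|---|---|---|---|---|
| 4.1, 6.1.2.1, 9.1 | 35% | 50-55% | 80 − 35 = 45 | 50 − 10 = 40 to 55 − 5 = 50 |
| 6.1.1 (diet B) | 30-35% | 55% | 80 − 35 = 45 to 80 − 30 = 50 | 55 − 10 = 45 to 55 − 5 = 50 |
| 2.1, Table 1 | 30-40% | 45-55% | 80 − 40 = 40 to 80 − 30 = 50 | 45 − 10 = 35 to 55 − 5 = 50 |

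Under the Section 4.1 and 9.1 targets the carbohydrate midpoints differ by 52.5 − 7.5 = 45 points, the same as the lipid gap. With energy and protein share matched, every point of energy taken from carbohydrate has to reappear as fat.

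**2. MCT.** It is 25% of lipid energy (Sections 1.1, 4.1, 6.1.1), so 0.25 × 80% = 20% of total energy, in one arm only during the admission. Section 6.1.2 gives the same 20%.

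**3. What the TUG model identifies.** The Section 9.4.2 ANCOVA has the form: day-7 TUG = intercept + b × arm + c × age + d × day-1 TUG. There is one randomised contrast, and ketone level, fat, carbohydrate and MCT all move with it. The coefficient b is their combined effect. No arm varies ketosis at similar fat and carbohydrate, and the model has no ketone term. Adding one would not help: beta-OHB is measured after randomisation and is largely set by arm. Table 1 lists 0 to 0.2 mM for SAD and a mean of 1.15 mM on a ketogenic diet in an earlier PD trial. If this trial performs similarly, the arms differ by at least about 1.15 − 0.2 = 0.95 mM.

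**4. What the plan offers on ketosis itself.** Beta-OHB is drawn twice daily on days 1-6, once on day 7 and once at week 3. TUG is measured daily on days 1-7 and at week 3. The data for a within-person analysis therefore exist: with 14 evaluable participants in the MCT-KD arm, 14 × 7 = 98 paired inpatient days. Section 6.1.1 describes the time series as a goal. Section 9.4.3, however, plans correlations among outcome variables, while Section 4.1 lists beta-OHB under the independent variable. No analysis of beta-OHB against TUG is named. A pooled correlation would largely restate the arm contrast in step 3. Within the MCT-KD arm, ketones are expected to rise with time on diet, and Section 4.2 expects learning on TUG.

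**5. What is unaffected.** The sample size reproduces. With a difference of 4.5 s, SD 4 s and two-sided alpha 0.0492, the noncentral t gives 78.4% power at 13 per group and 81.5% at 14. That is 28 evaluable; 28 / 0.9 = 31.1, rounded up to 32 for equal groups. These figures concern the diet contrast and do not depend on its interpretation.

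**The case against.** The strongest defence is that nutritional ketosis is the protocol's shorthand for the diet. Section 9.1 glosses it as "ketogenic diet with 80% lipid including MCT oil, 10-15% protein, 5-10% carbohydrate", sets the null between the ketosis-diet group and the usual-diet group, and states the comparator by macronutrients. Section 9.4.2 speaks of diet. The synopsis also states the hypothesis as MCT-KD against SAD. Section 4.2 concedes that the benefit of a low-carbohydrate diet may involve more than ketosis and lists other mechanisms. It also poses a question about different ketone values on serial measurements, which is a within-person question.

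Much of this stands. A reader might infer that any TUG gain would be credited to ketosis with no support at all. The documents do not bear that out, because the operative analysis language is already diet against diet and the alternative explanations are openly stated. A reader might also take the benefit that a previous PD trial reported at a mean beta-OHB of 0.31 mM as evidence that a TUG gain would arise without ketosis. That benefit was cognitive, and Section 2.1 reports no motor difference in the same trial. The walking-speed reports at low or undetectable ketosis in Section 4.2 are described as anecdotal.

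It is also fair that the confounder Section 2.1 develops at length is protein and levodopa absorption, which this trial controls, and that energy is matched. Comparing a whole ketogenic diet with usual diet is a legitimate choice for a feasibility pilot.

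The defence does not reach three things: the Section 2.1 sentence on what the comparison tests, the Section 4.3 sentence on composition, and the mechanism-specific hypothesis in Section 4.1, which ties the effect to reaching ketosis and so cannot be read as shorthand for a diet.

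**Conclusion.** The point holds as a matter of attribution. The randomised contrast estimates the effect of the whole MCT-KD diet against SAD. The arms differ by about 45 points of energy in lipid (40 to 50 across the stated SAD compositions), by 40 to 50 points in carbohydrate (35 to 50 across them), and by about 20% of energy as MCT. No part of a TUG difference can be assigned to ketosis by randomisation. The Section 2.1 objective and the Section 4.3 composition claim are wrong as written, except for protein and energy.

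This rests on the planned macronutrient targets; achieved intake could differ. It concerns a secondary outcome and the exploratory objectives. A reader might infer that the trial needs another arm or that its comparison is invalid. Neither follows: the diet-versus-diet estimate, the TUG ANCOVA, the sample size and the primary feasibility outcome are sound on this point.

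**What to change.** 1. Reword the Section 2.1 objective, the secondary objective in Section 1.1, the objectives in Section 3, the hypothesis in Section 4.1 and the TUG hypothesis in Section 9.1 as the effect of MCT-KD versus SAD, in line with Section 9.4.2.
2. In Section 4.3, limit the claim of similar composition to matched protein and energy.
3. Reconcile the SAD composition across Sections 2.1 (Table 1), 4.1, 6.1.1 and 9.1.
4. In Section 9.4.3, name an analysis of beta-OHB against TUG, for example a within-subject mixed model in the MCT-KD arm with study day included. Label it exploratory and non-randomised.
5. State in Section 9 that any claim about ketosis itself rests only on that analysis and is reported separately from the randomised diet effect.

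The cost is protocol and SAP wording plus one exploratory model on data already collected. No participant, visit or arm is added and power does not change. The price is a narrower conclusion: a positive TUG result would support the diet, not ketosis as its cause.
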